### 3.3.5 Issues in data collection

The following are data collection issues that have been identified during the conduct of the study, and for which some considerations will be done in the statistical analysis:

- A) No severity grade recorded for Erythema and Induration (Reactogenicity – Baseline and Early eCRF, and Reactogenicity – Daily Log eCRF):** Because of a programming error, missing values were allowed and not automatically queried when entered in some fields of the Reactogenicity - Daily Log eCRF. The fields affected were the severity grade for Erythema/redness and the severity grade for Induration/swelling, which in both eCRFs appear after the question “Is vaccine-related erythema or induration visible?”. The issue resulted in two different patterns of responses, both consistent with the absence of any of these events, being entered by site personnel, as described below:

	Is vaccine-related erythema or induration visible?	Erythema and redness largest diameter	Induration/swelling largest diameter	Erythema /redness	Induration/ swelling
Pattern A	No	[blank]	[blank]	None	None
Pattern B	No	[blank]	[blank]	[blank]	[blank]

For analysis purposes, response pattern B will be considered equivalent to pattern A. This is, for cases showing response pattern B, the absence of severity grade in the corresponding fields will be assumed to indicate that no event was observed, provided that the response that the response

to the question “Is vaccine-related erythema or induration visible?” is “No” and that no other related information (such as diameter) was entered. For these cases, a value of “None” for the severity field will be inputted, for analysis purposes.

**B) Surface excluded from criteria for evaluation of Erythema and Induration Severity (Reactogenicity – Baseline and Early eCRF, and Reactogenicity – Daily Log eCRF):**

Following Protocol Version 4.0, which excludes percent of the affected surface area as one of the criteria for evaluation of Erythema/redness and Swelling/induration (Table 6. Toxicity Grading Scale – Solicited Local Reactions), this variable, although collected for some participants, will not be included in analyses. Severity grades for Erythema/redness and Swelling/induration will be reported as entered in the database by site personnel, noting that effort has been made to detect, query, and reconcile cases where responses to related fields do not show the expected consistency.

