## 9 SAFETY SECONDARY OBJECTIVES

### 9.1 Solicited Local and Systemic Adverse Events (Reactogenicity)

(Secondary) Endpoint: All solicited AEs reported during a 7-day follow-up period after meningococcal vaccination.

Per protocol, solicited injection site (local) and systemic reactogenicity adverse events are intended to be collected from time of study meningococcal vaccination through 7 days after each vaccination. Reactogenicity is intended to be first assessed about 30 minutes post-vaccination, then routinely assessed during the first four days post-vaccination and again on Day 8 Visit (Study Visit 2, scheduled at Day 8 with + 3-day window). For instances where there is reactogenicity of grade 2 or higher at the fourth day post-vaccination (Day 5), then daily assessments are intended to continue, until resolution or the severity of the reactogenicity is grade 1 (Mild). Severity grade for solicited AEs is recorded as none, mild, moderate, Severe and Potentially Life Threatening. Systemic AEs include Body temperature, Irritability, Drowsiness/Lethargy, Decrease Eating/Anorexia, Vomiting and Feverishness. Local AEs include erythema/redness (severity and largest diameter in cm), induration/swelling (severity grade and largest diameter in cm), and pain and/or tenderness.

For this safety endpoint, all reactogenicity symptoms reported after receipt of meningitis vaccination at Study Day 1 to Day 7 (including early assessment post-vaccination) will be included, as well as symptoms reported for Study Day 8, as long as the Day 8 assessment visit occurred within the specified visit window. Symptoms will be reported according to the Study Day for which they were reported in the Reactogenicity - Baseline and Early and Reactogenicity - Daily Log eCRFs.

Analysis Set: mITT Analysis Set

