Approach: For each systemic and local solicited AE, the maximum severity reported by participants after vaccination, as collected in the Reactogenicity – Daily Log eCRF will be summarized. The number and percentage of subjects reporting each AE will be presented in tables by Symptom, Maximum Severity and vaccine arm. Additionally, the number and percentage of subjects reporting any Systemic Solicited Symptom, any Local Solicited Symptom will be calculated and reported by maximum Severity and vaccine arm. For calculation of percentages, the denominator is the number of subjects in the analysis set (excluding those missing all post-vaccination assessments for the symptom). For local AEs that report largest diameter, summary statistics (mean and SD, median and IQR, range) will be presented.

For each systemic and local solicited AE, bar plots describing the classification (proportion) of participants by the maximum severity of the AE reported, by Study Group, will be produced.

Additional Tables/Listings: All systemic and local solicited AEs will be summarized at the event level, by collection time (Day 1 early assessment and Days 1-8 post-vaccination), Symptom, Severity. For calculation of percentages, the denominator is the number of subjects in the analysis set (excluding those missing assessments for the day and symptom). Summary statistics for largest diameter of local AEs, as appropriate, will also be reported.

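### SAP 9.1 contradicts itself on the data source for maximum reactogenicity severity: the endpoint paragraph uses both reactogenicity forms, the Approach names only the Daily Log

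*SAP*

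**What the plan says.** All of the conflicting text is in SAP 9.1.

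- **Timing of assessments.** "Reactogenicity is intended to be first assessed about 30 minutes post-vaccination". Routine assessments follow over the first four days and again at the Day 8 visit.
- **Endpoint paragraph.** For this secondary safety endpoint, "all reactogenicity symptoms reported after receipt of meningitis vaccination at Study Day 1 to Day 7 (including early assessment post-vaccination) will be included". Day 8 symptoms are added only if the Day 8 visit took place within its window. Symptoms are assigned to the study day for which they were "reported in the Reactogenicity - Baseline and Early and Reactogenicity - Daily Log eCRFs".
- **Approach.** For each symptom, the maximum severity after vaccination "as collected in the Reactogenicity – Daily Log eCRF will be summarized". The any-systemic and any-local tables and the bar plots are also organised by maximum severity. The percentage denominator is the analysis set, "excluding those missing all post-vaccination assessments for the symptom".
- **Additional tables.** All solicited events are also summarised at event level, "by collection time (Day 1 early assessment and Days 1-8 post-vaccination", and by symptom and severity.

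Two other places bear on the point. SAP 3.3.5, items A and B, discusses erythema and induration grading under the label "Reactogenicity – Baseline and Early eCRF, and Reactogenicity – Daily Log eCRF", and item A says the severity fields are present on both forms. Protocol 5.2 has solicited local and systemic events recorded during the 30-minute observation in both age groups. Protocol 9.6 asks for the maximum severity over all 7 days and names no form.

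**The concern.** The endpoint paragraph and the Approach describe the same secondary endpoint but draw on different sets of forms. A programmer who follows the first pools both forms. One who follows the second reads only the Daily Log. The two can obtain different counts from the same database.

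The tables affected are the participant-level reactogenicity tables, which most readers will treat as the main safety result. Under SAP 3.1, secondary endpoints go into the two age-group reports for WHO. On the literal Approach, an immediate reaction that had gone by the first daily record would leave the infant counted as reaction-free in the main table, while the same event appears in the by-time table of the same report.

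**Working it through.** The plan gives no figure to reproduce and no arithmetic applies. The check sets the rules side by side and follows example records through them.

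**Step 1. Are these two separate forms, and does the early one hold gradable data?** Yes. SAP 3.3.5 treats them as separate forms and says both contain severity fields for erythema and induration. SAP 9.1 names them separately in the endpoint paragraph. The early form is therefore a source of grades that the SAP regards as analysable.

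**Step 2. What does each rule admit?**

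| Part of SAP 9.1 | Early assessment | Form named |
|---|---|---|
| Endpoint paragraph | Included explicitly | Baseline and Early; Daily Log |
| Approach, maximum severity | Not mentioned | Daily Log |
| Approach, denominator | Any post-vaccination assessment | None named |
| Event-level table | Its own collection time | None named |

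**Step 3. Follow hypothetical infants through the rules.** These cases are illustrations and are not taken from trial data. The third column is the literal reading of the Approach.

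| Infant | Maximum under endpoint paragraph | Maximum under Approach |
|---|---|---|
| Mild erythema at the early assessment, none in the Daily Log | Mild | None |
| Moderate at the early assessment, mild in the Daily Log | Moderate | Mild |
| Mild at the early assessment, mild or worse in the Daily Log | Same as Daily Log | Same |
| Early assessment done, no Daily Log record | Early grade | No grade available, yet in the denominator |

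Only the first, second and fourth patterns give different results. A participant's maximum changes only if the early grade is not matched or exceeded in the Daily Log. The any-local and any-systemic tables inherit the difference when no other symptom of that class reaches the same grade.

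**Step 4. Which symptoms are exposed?** Separate severity fields on both forms are documented for erythema and induration. Protocol 5.2 has solicited local and systemic events recorded in the 30-minute observation, so other symptoms may be exposed too. For feverishness, SAP 3.3.5 item C mentions collection on the Daily Log only, so no effect is shown.

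**Step 5. Can the size be derived?** No. It would need the number of infants whose early grade exceeds every Daily Log grade, and neither document reports it or a rate from which it follows.

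**The case against.** The strongest reply is that the Approach names the Daily Log without saying that it is the only source, and that its surroundings favour the inclusive reading. The endpoint paragraph includes the early assessment outright, the denominator is not tied to one form, and Protocol 9.6 names no form. Immediate reactions are also reported under either reading, because the event-level table gives the early assessment its own collection time. That table and the maximum-severity table count different things, so their totals need not agree in any case. Finally, the exposed set is narrow. Day 1 has its own daily record besides the early one, and under Protocol 6.1 the memory aid runs from the time of vaccination, so many early reactions may be captured again.

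Most of this stands. It limits the consequence and rules out a stronger inference that a reader might draw, namely that early-only reactions drop out of the secondary endpoint. The endpoint paragraph keeps them in, so the documents show a conflict and not a settled exclusion. The reply does not remove the conflict. The sentence that generates the participant-level tables names one form, while the paragraph that defines the endpoint names two. The unrestricted denominator makes the literal reading worse, because an infant with only an early assessment could count in the denominator and never in the numerator.

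**Conclusion.** The point holds as an internal contradiction in SAP 9.1, and it is minor. If the Approach is programmed as written, reactions recorded only at the early assessment, or at a higher grade there, are missing or under-graded in the maximum-severity, any-local and any-systemic summaries. They remain within the endpoint as defined and in the by-time table.

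The size is unknown. A reader might try to gauge it from the Phase 2 local reaction frequencies of 1.3, 3.0 and 0.7% in Protocol 1.1.2. Those figures cover all solicited local reactions, not those seen only at 30 minutes, and they span two formulations and a different comparator vaccine. They do not support an estimate.

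The conclusion assumes that the form name in the Approach is followed literally. Protocol 9.2 makes the safety analysis descriptive, with no hypothesis test, so no decision rule, power figure or type I error rate is affected.

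**What to change.** Revise the Approach sentence in SAP 9.1 so that maximum severity is the highest grade across (a) the post-vaccination records of the Baseline and Early form, leaving out its pre-vaccination baseline, and (b) the Daily Log, with Day 8 counted only when the visit was within its window. The baseline exclusion is needed because Protocol 6.1 also calls for a reactogenicity assessment before vaccination. The Day 8 condition keeps the sentence in line with the endpoint paragraph. Apply the same definition to the any-local and any-systemic tables and the bar plots.

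If the team does intend to leave the early assessment out of the maximum, it should say so, give the reason, and amend the endpoint paragraph and the denominator to match.

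The cost is one SAP sentence, with no new data collection. It is best done before the tables are run, since SAP 3.1 requires changes to the specified analyses to be documented and labelled as post hoc when reported.

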5.3 Planned Study Visits

5.3.1 Follow-up

Visit #2 (Day 8 + 3 days after study meningococcal vaccination)

Study subjects will return for follow-up evaluation to the clinical study site approximately 7 days following meningococcal vaccination. Alternatively, a home visit may be performed by a medically qualified site personnel. At this visit, investigator or delegate will perform the following:

- Review of solicited and unsolicited AEs experienced during the initial 4 days after vaccination, assisted by review of home visit worksheets which are completed by a daily visit by field workers during the first 4 days following vaccination
- Assessment of any ongoing solicited AEs on Day 8 post-vaccination (note that all ongoing solicited AEs beyond Day 8 must be followed up daily by site staff until resolution)
- Medical interview of subject’s parents/guardians to assess any unsolicited AEs, SAEs since previous study visit
- Collection of concomitant medications and vaccinations
- Physical examination including assessment of vital signs (heart rate and respiratory rate) and axillary body temperature
- Schedule Visit 3, approximately 28 days after vaccination

Visit #3 (Day 29 + 7 days after study meningococcal vaccination)

Study subjects will return for follow-up evaluation to the clinical study site approximately 28 days following meningococcal vaccination. At this visit, investigator or delegate will perform the following:

- Review of unsolicited AEs experienced during the 28 days after vaccination using home visit worksheets
- Medical interview of subject’s parents/guardians to determine if any unsolicited AEs or SAEs occurred and if any concomitant medication or vaccines were received since the last study visit.
- Check any ongoing AEs and concomitant medications since the last study visit and record resolution date (the end date), if available in the source documents or eCRFs.
- Physical examination including assessment of heart rate, respiratory rate, and axillary body temperature

- Collection of blood sample (approximately 10 mL) for serology testing.
- Schedule Visit 4, approximately 6 months after vaccination

Visit #4 (Day 181 ± 14 days after study meningococcal vaccination)

Study subjects will return for follow-up evaluation to the clinical study site approximately 6 months following meningococcal vaccination. At this visit, investigator or delegate will perform the following:

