7.3 Reporting Procedures

Solicited injection site and systemic reactogenicity events will be documented and reported from the time of study vaccination through 7 days after study meningococcal vaccination. *Note that community field workers will only perform the daily visits to complete the documentation of axillary body temperature, size of swelling/induration, and other reactogenicity during the initial 4 days following vaccination. The remaining days prior to Visit 2 may not be documented if the events are grade 1 or resolved, especially from illiterate families, and this will not be considered a protocol deviation. For instances where there is reactogenicity of grade 2 or higher at the fourth day post-vaccination (Day 5), then field workers will continue the daily visits to complete the memory aid document until resolution or the severity of the reactogenicity is grade 1.*

However, through interviewing the parent/guardian, reactogenicity events through 7 days after study meningococcal vaccination are intended to be collected. Unsolicited non-serious AEs will be documented and reported from the time of study meningococcal vaccination through 28 days after study meningococcal vaccination. SAEs will be documented and reported from the time of enrollment through approximately 2 years after study meningococcal vaccination.

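### The by-day reactogenicity percentages for Days 6-7 rest on a denominator that depends on the Day 5 outcome and can be substantially inflated unless the parent interview fills those days

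*SAP*

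**What the plan says.** SAP 9.1 describes two summaries of solicited reactions in the mITT set. The main one is maximum severity per infant; its denominator leaves out only infants with no post-vaccination assessment at all for the symptom. The second, under Additional Tables/Listings, is broken down "by collection time (Day 1 early assessment and Days 1-8 post-vaccination"), and there "the denominator is the number of subjects in the analysis set (excluding those missing assessments for the day and symptom").

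The same section gives the assessment schedule. Reactions are checked about 30 minutes after vaccination, "then routinely assessed during the first four days post-vaccination and again on Day 8 Visit". With vaccination on Day 1, the fourth day after it is Day 5. Daily assessment continues after that only for infants at grade 2 or higher on Day 5, until the reaction resolves or falls to grade 1. Protocol 5.4 and 7.3 state the same rule.

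For everyone else, Protocol 7.3 says: "The remaining days prior to Visit 2 may not be documented if the events are grade 1 or resolved". This is not counted as a protocol deviation. The section then adds that, by interviewing the parent or guardian, "reactogenicity events through 7 days after study meningococcal vaccination are intended to be collected".

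Protocol 9.6 commits to a severity summary for each of Days 1-8 and, unless the SAP says otherwise, to no imputation of missing data.

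**The concern.** Days 6 and 7 fall between the last routine home visit and Visit 2. On those days an infant is certain of a scheduled assessment only if a grade 2 or higher reaction was present on Day 5. A denominator that drops infants without a record then keeps the reacting infants and loses many of the non-reacting ones, so the percentage with any reaction is pushed upward.

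No other rule in the SAP closes the gap. SAP 3.3.5 A reads blank severity grades as none only for erythema and induration, and only when the visibility question was answered No. It does not cover a day with no record.

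At stake is the apparent frequency of late reactions in a safety table. Secondary safety results go into the reports intended for WHO (SAP 3.1), where a reader could take a percentage based on a few selected infants for a rate in the vaccinated population.

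**Working it through.** The documents give no Day 6-7 rate or denominator, so there is no figure to reproduce. The check asks how far the stated rule can move the percentage.

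**Inputs**
- N = 400, the planned NmCV-5 arm in each age group (SAP Table 1). All are taken as assessed on Day 5.
- g = infants still visited on Day 6 under the grade 2 rule, taken as still reacting (assumption; 1, 4 or 8).
- f = share of the other infants with a Day 6 record from the Visit 2 interview (assumption; 0 to 100%).
- b = reaction rate among those others (assumption; 0 or 1%).

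**Formulas**
- Shown under SAP 9.1: (g + f·b·(N − g)) / (g + f·(N − g))
- With complete records: (g + b·(N − g)) / N
- Recorded reactions over all infants assessed on Day 5: (g + f·b·(N − g)) / N

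**Results for g = 4**

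| f | Shown, b = 0 | Shown, b = 1% | Day 5 denominator, b = 1% |
|---|---|---|---|
| 0 | 4/4 = 100% | 4/4 = 100% | 4/400 = 1.0% |
| 5% | 4/23.8 = 16.8% | 4.198/23.8 = 17.6% | 1.05% |
| 25% | 4/103 = 3.9% | 4.99/103 = 4.8% | 1.25% |
| 50% | 4/202 = 2.0% | 5.98/202 = 3.0% | 1.5% |
| 90% | 4/360.4 = 1.1% | 7.564/360.4 = 2.1% | 1.9% |
| 100% | 4/400 = 1.0% | 7.96/400 = 2.0% | 2.0% |

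With complete records the rate is 1.0% for b = 0 and 7.96/400 = 1.99% for b = 1%. For b = 0 the Day 5 denominator gives 1.0% at every f. For other g with b = 0 and f = 0, the table shows 100% against 0.25% (g = 1, 400-fold) or 2.0% (g = 8, 50-fold). At f = 50% the inflation is about 2-fold for all three values of g.

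**Records of reactions only.** If the interview creates a record only when a reaction is reported, each one enters numerator and denominator together. With g = 4 and b = 1% the table shows 7.96/7.96 = 100% against 1.99%.

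**How many infants might trigger visits.** Protocol 1.1.2 reports one non-mild solicited reaction in 375 children given two doses: 1/750 = 0.13% per dose, or 1/375 = 0.27% per child. For 400 infants that is 0.53 to 1.07 expected, with a 41% to 66% chance of at least one. For the 200 infants in a control arm it is 0.27 to 0.53 expected, with a 23% to 41% chance. The trigger needs grade 2 or higher specifically on Day 5, which lowers these. Phase 2 children were older (12-16 months), and fever is a listed side effect of the live vaccines given alongside here (Protocol 1.3.1), so the rate could also be higher; hence the range of g up to 8. If the interview adds little, one arm could show 1/1 while the other has no denominator.

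**The case against.** The strongest reply is that Protocol 7.3 does not leave Days 6-7 to the triggered visits. It intends reactions through 7 days to be collected by interview, and SAP 9.1 assigns each symptom to the study day for which it was reported, so a later interview can fill those days. Protocol 5.2 speaks of home visits for 4 to 7 days, and the schedule of events lists a 7-day memory aid. A reader might infer that the percentages use only infants still visited and are bound to be grossly inflated. The documents do not support that: the wording on undocumented days is permissive, and at 90% capture the inflation is about 1.1-fold.

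This stands as a limit on the claim, but does not remove it. The interview is described as collecting events, and no text requires an entry of no reaction for each day. The Visit 2 procedures in Protocol 5.3.1 list "Review of solicited and unsolicited AEs experienced during the initial 4 days after vaccination" and anything ongoing on Day 8, without naming Days 6-7. Protocol 6.1 has the memory aid run for at least 4 days. How completely Days 6-7 are recovered is left open.

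Two further points stand. A visited infant is presumably assessed for every symptom, and may have improved by Day 6, so a cell for a symptom that did not trigger the visit could read 0%. The upward bias applies to any reaction and to the triggering symptom. And the table is additional and descriptive; Protocol 9.2 plans no safety hypothesis tests.

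**Conclusion.** The point holds as a conditional defect. On Days 6-7 the stated denominator depends on the Day 5 outcome, and the percentage with any reaction can be substantially inflated unless interview records are near complete and include infants without reactions. Over the range examined the inflation runs from none to 400-fold. The documents give neither the number of triggered infants nor the interview capture, so no single figure is defensible. The illustration of 100% or 2.0% against 1.0% rests on 4 of 400 infants still visited and reacting and no reaction among the others.

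A reader might also infer that the secondary safety endpoint is compromised. It is not compromised in this way: a missing Day 6 or 7 does not shrink the maximum-severity denominator, because an infant leaves it only if every post-vaccination assessment for the symptom is missing. The correction is worth making because it concerns a stated rule and costs little.

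**What to change.** Amend the by-day table in SAP 9.1:

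- Keep the present denominator for the 30-minute assessment, Days 1-5 and Day 8.
- For Days 6-7 show the count of infants with each reaction at any recorded grade, and beside it the number with a record for that day.
- Compute any Day 6-7 percentage over all mITT infants assessed on Day 5, not only those with a Day 6-7 record.
- Footnote that Days 6-7 were not routinely assessed and that undocumented days are counted as no reported reaction of grade 2 or higher.

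This keeps the Days 1-8 summary promised in Protocol 9.6 and retains grade 1 and new-onset reactions recovered by interview. The resulting percentage can understate unrecorded grade 1 reactions: in the example with b = 1% and no interview records it reads 1.0% where complete records would give 1.99%, while the present rule reads 100%. The footnote makes that limit visible.

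The descriptions of home visits (4 days, or 4 to 7 days), the memory aid (7-day, or at least 4 days) and the Visit 2 review should also be reconciled, so that it is clear what Day 6-7 data exist.

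The cost is a few lines of SAP text, a table footnote and minor programming, with no change to data collection. Under SAP 3.1 a change to a specified analysis is documented and reported as post hoc.
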